6.6 Clinical Adverse Events

During the course of this study the team will follow the protocol laid out in the IRB. If for any reason the protocol needs changed, appropriate modifications will be submitted to the IRB for permission/approval. Compliance meetings will occur annually to assure that data and confidentiality are being maintained. Clinical adverse events (AEs) will be monitored throughout the study.

6.7 Adverse Event Reporting

All on-site SAEs (AHN or related sites) will be reported to the IRB in accordance with IRB policies. AEs that are not serious will be summarized in narrative or other format and submitted to the IRB at the time of continuing review.

6.8 Definition of an Adverse Event

An adverse event is any untoward medical occurrence in a subject who has received an intervention (drug, biologic, or other intervention). The occurrence does not necessarily have to have a causal relationship with the treatment. An AE can therefore be any unfavorable or unintended sign (including an abnormal laboratory finding, for example), symptom, or disease temporally associated with the use of a medicinal product, whether or not considered related to the medicinal product.

All AEs (including serious AEs) will be noted in the study records and on the case report form with a full description including the nature, date and time of onset, determination of non-serious versus serious, intensity (mild, moderate, severe), duration, causality, and outcome of the event.

The risks associated with the study arm, which is immediate weightbearing following foot and ankle surgery include the potential for the following:

- Excessive Pain with weightbearing on the surgical extremity
- Potential wound complications associated with surgical incision sites
- Possible hardware failure
- Possible non-union, mal-union, or delayed union during osseous healing
- Possible non-healing or delayed healing of soft tissue structures

6.9 Definition of a Serious Adverse Event (SAE)

An SAE is any adverse drug experience occurring at any dose that results in any of the following outcomes:

• Death,

- A life-threatening event (at risk of death at the time of the event),
- Requires inpatient hospitalization or prolongation of existing hospitalization, a persistent or significant disability/incapacity, or a congenital anomaly/birth defect in the offspring.

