PROTOCOL COVER SHEET

Immediate Weight-bearing Verses Non-Weight-bearing after Foot & Ankle Surgery: A Prospective Analysis

04/29/2019

PRINCIPAL INVESTIGATOR [name], DPM, FACFAS

CO-INVESTIGATORS [name], DPM [name], DPM, FACFAS THE FOOT & ANKLE INSTITUTE STEEL VALLEY ORTHOPAEDIC AND SPORTS MEDICINE [name] [contact]

Email: [contact]

ABBREVIATIONS AND DEFINITIONS OF TERMS

NWB	Non-weight-bearing
WB	Weight-bearing
AE	Adverse event
SAE	Serious adverse event

ABSTRACT

In recent years, significant attention has been placed on the safety and efficacy of immediate weight-bearing following foot and ankle surgery. Returning patients to their previous activities as quickly as possible following surgery is always in the mind of providers, but the question of when has been difficult to answer.

Objectives:

The primary objective is to assess if immediate weight-bearing following foot and ankle surgery will yield equivalent, if not superior outcomes to the traditional non-weight-bearing post-operative course, while avoiding the undesirable effects commonly experienced during extended periods of non-weight-bearing. This will be determined by serial radiographs and/or other appropriate imaging modalities, physical exams and using patient self-reported pre- and post-operative SF-36 and AOFAS questionnaires.

Study Design:

Prospective, randomized controlled trial.

Setting/Participants:

Patients will be consented from 5 sites West Penn Hospital, Jefferson Regional Hospital, Forbes Regional Hospital, Bethel Park Surgery Center, and Monroeville Surgery Center and the level of care will include both inpatient and outpatient.

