The subjects will be identified/recruited during clinic hours as patients requiring an elective or traumatic foot and ankle surgery. During the clinic hours the primary investigator and/or the co-investigator will obtain full consent from the patient. We will recruit a minimum of 115 participants into each of two study arms, an immediate weight-bearing arm and a non-weight-bearing arm, so 230 participants will be included. Patients will be eligible if they are undergoing elective or traumatic foot and ankle surgery. Exclusion criteria will include any patient less than 18 years of age & over 89, history of foot or ankle surgery on the surgical limb, any degree of diagnosed peripheral neuropathy or peripheral vascular disease, infection, and/or unwillingness to participate at random in one of the two study arms.

Study Interventions and Measures:

We will be assessing the difference in two groups; immediate protected weight-bearing in a CAM walking boot vs strict non-weight-bearing for 6 weeks following foot and ankle surgery. Monitoring will be done by way of clinical follow-up, serial radiographs and/or other appropriate imaging modalities, and patient reported outcomes by way of AOFAS and SF-36 surveys.

Surgical procedures performed on patients included in the study will vary, as will the outcome measures for each procedure. Osseous fusions, including both elective joint fusions and bone healing following trauma, will be assessed by both clinical and radiographic evaluation. Soft tissue procedures, including elective stabilization and traumatic soft tissue repairs, will be assessed clinically and with imaging modalities

deemed appropriate. Complications during the perioperative and post-operative periods, such as non-union, infection, etc. will be included in the outcomes. All participants will also complete AOFAS and SF-36 surveys in the pre-operative and post-operative periods. We will also include return to work, activity, sport, etc. where appropriate.

Study Phase	Screening	Surgery	Post-op 2-3 w	Post-op 6-8 w	Post-op 3 m	Post-op 6 m	Post-op 1 yr	Post-op 2 yr	Unscheduled Visits
Visit Number	1		2	3	4	5	6	7	
Informed									
Informed Consent/Assent	x								
Review Inclusion/Exclusion									
Criteria	х								
Randomization	x								
Demographics/PMH	x								
Physical Examination	x		x	x	x	x	x	x	x
Adverse Event Assessment			x	x	x	x	x	x	x
Radiographs/Imagining	х		x	x	x	x	x	x	x
Complete AOFAS/SF- 36 survey	x			x	x		x	x	

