6.10 IRB/IEC Notification of SAEs and Other Unanticipated Problems

The Investigator will promptly notify the IRB of all on-site unanticipated, serious Adverse Events that are related to the research activity. Other unanticipated problems related to the research involving risk to subjects or others will also be reported promptly. Written reports will be filed using the IRB system and in accordance with the IRB SOP#11. External SAEs that are both unexpected and related to the study intervention will be reported promptly after the investigator receives the report.

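### The SAE definition in 6.9 is worded for a drug and has no re-operation criterion, so a day-case revision is by default non-serious and reaches the IRB in the continuing-review summary

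*Combined protocol and SAP*

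**What the plan says.** The abstract describes the comparison as "immediate protected weight-bearing in a CAM walking boot vs strict non-weight-bearing for 6 weeks following foot and ankle surgery". No study drug is given in either arm.

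Section 6.9 defines seriousness in these terms: "An SAE is any adverse drug experience occurring at any dose that results in any of the following outcomes". Two of the outcomes are death and a life-threatening event. The rest of the list reads "Requires inpatient hospitalization or prolongation of existing hospitalization, a persistent or significant disability/incapacity, or a congenital anomaly/birth defect in the offspring". Nothing follows it.

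The neighbouring sections are worded more broadly. Section 6.8 defines an adverse event for a drug, a biologic or any other intervention. Section 6.9.1 also names other interventions in its heading, and it grades causality against the study intervention.

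Reporting to the IRB runs on three routes:

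- Section 6.7 sends every on-site SAE to the IRB under that body's own policies.
- For everything else, 6.7 says "AEs that are not serious will be summarized in narrative or other format and submitted to the IRB at the time of continuing review".
- Section 6.10 says "The Investigator will promptly notify the IRB of all on-site unanticipated, serious Adverse Events that are related to the research activity", and adds prompt reporting of other unanticipated problems that put subjects or others at risk.

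Section 6.8 lists the expected risks of immediate weight-bearing. They are excessive pain, wound complications, "Possible hardware failure", disturbed bone union and disturbed soft-tissue healing. Section 7.3.2.6 repeats the list. On setting, the abstract says "the level of care will include both inpatient and outpatient", and two of the five sites are surgery centers.

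**The concern.** The definition that decides which IRB route an event takes does not fit this trial, in two respects. Its opening refers to a drug and a dose, and there is neither. Its outcomes also omit the form in which several of the listed harms would become serious, namely an unplanned return to surgery. A failed fixation, a non-union or a broken-down wound may need revision without an inpatient stay, and outpatient care is in scope.

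At stake is how quickly anyone outside the study team sees such an event. Under 7.3.1 the principal investigator carries the ongoing safety monitoring, and study progress goes to the IRB once a year. The serious or non-serious label therefore largely sets the speed of independent sight of these events. Two investigators could also label the same revision differently, because the text gives them no rule for it.

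**Working it through.** The plan states no figure on this point. The check is a trace of one event through the rules: an outpatient revision for hardware failure, non-union or wound breakdown.

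**Step 1: does the opening of 6.9 apply?** Read literally, no, because no drug is given. Read with 6.8 and 6.9.1, yes. The remaining steps take the generous reading.

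**Step 2: does an outcome in 6.9 apply?**

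| Outcome in 6.9 | Met by an outpatient revision? |
|---|---|
| Death | No |
| Life-threatening event | Not ordinarily |
| Inpatient admission or longer stay | No, by construction |
| Persistent or significant disability | Only if the investigator judges it so |
| Birth defect | No |
| Unplanned re-operation | Not on the list |
| Important medical event | Not on the list |

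No other section adds a criterion. The default is non-serious.

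**Step 3: which IRB route follows?** Under 6.7 a non-serious event goes into the continuing-review summary. If continuing review is the annual submission described in 7.3.1, the wait could be up to about a year.

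**Step 4: is there a faster route?** Under 6.10 prompt notice of an SAE requires three things together: unanticipated, serious and related. The other route in 6.10 needs no seriousness but still requires an unanticipated problem. Hardware failure, non-union and wound complications are all listed beforehand in 6.8 and 7.3.2.6, so a single case would not ordinarily qualify. An unexpected frequency or severity might.

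**Step 5: does the outside review in 7.3.1 close the gap?** It is one look, after 10 patients per arm are enrolled: 2 × 10 = 20 patients. At the planned size, 230 − 20 = 210 patients remain, and no later outside look is described for them. The look is timed by enrolment rather than follow-up, so late events such as non-union may not yet be visible. Its list of complications includes non-union, mal-union, uncontrolled pain and wound complications. Hardware failure and re-operation are not named. It is also not a report to the IRB.

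**Step 6: would correcting 6.9 alone be enough?**

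- *Opening corrected only:* the step 2 table is unchanged and the event is still non-serious.
- *Opening corrected and re-operation added:* the event becomes an SAE and takes the SAE route of 6.7. Its timing then depends on IRB policies that are not in the documents. Prompt notice under 6.10 still fails on the word unanticipated.
- *6.7 and 6.10 aligned as well:* route and timing are stated whether or not the event is a listed risk.

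**Step 7: are the data lost?** No. Section 6.8 puts every AE on the case report form with seriousness, intensity, causality and outcome. Section 4.4 records unscheduled visits for complications. Section 6.2 makes complications and osseous healing secondary endpoints, and 6.4.1 compares them between arms by chi-square. None of these uses the SAE label.

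**The case against.** The strongest reply is that the drug wording is leftover template text whose intended meaning is clear from 6.8 and 6.9.1. On this view the trial's safety evidence does not rest on the SAE label: all events are recorded, complications are compared by arm, and the review in 7.3.1 looks at adverse events generally. The IRB policies and the SOP cited in 6.10 may also impose duties that the protocol does not repeat.

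Much of this stands. The intended reading of the opening is recoverable, and results are unaffected. The cited policies could not be checked. What does not fall away is the outcome list: even with the opening read as intended, it has no place for an unplanned re-operation.

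Some stronger readings are tempting, and the documents do not support them:

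- *That a published comparison of SAEs would hide failures and support an unjustified safety claim.* No SAE comparison is planned. The planned comparison is of complications and healing, without regard to seriousness.
- *That no event in this trial can be an SAE.* This follows only from reading the opening of 6.9 in isolation.
- *That a day-case revision is always non-serious and always waits for continuing review.* The disability criterion and the unanticipated-problem route leave some room for judgement.
- *That these are the harms immediate weight-bearing is most likely to cause.* Section 6.8 gives no likelihoods, and 7.3.2.7 says the risks exist under either regimen.
- *That most revisions would be day cases because two sites are surgery centers.* The site list does not show where revisions are done.

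**Conclusion.** The point holds as a defect in classification and in the speed of IRB reporting. It is more than clerical, because an investigator who follows 6.9 as intended would still class the re-operated form of several listed harms as non-serious. It should be corrected, but it does not threaten the endpoints or the between-arm comparison.

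Its size cannot be put as a number of events. The documents give neither a re-operation rate nor the share of revisions done without admission, and the conclusion depends on neither. It rests on three assumptions: that some revisions could be done as outpatient procedures, that risks listed in advance are ordinarily treated as anticipated, and that the IRB policies cited but not included do not already require faster reporting of such events.

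**What to change.** 1. In 6.9, replace the drug-and-dose opening with wording such as *an adverse event following the study intervention (either arm)*.
2. In 6.9, add the outcome *unplanned surgical intervention on the study limb, inpatient or outpatient*.
3. Reconcile 6.7 and 6.10 at the same time, so that they state the reporting route and timing for such events even when the event is a listed risk. Without this, the unanticipated condition in 6.10 still excludes them from prompt notice. Check the result against the IRB policies and the SOP that the protocol cites.
4. Within the existing complications endpoint in 6.2, count unplanned re-operation by arm. This needs no new data collection, since 4.4 and 6.8 already record the events.

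The cost is a protocol wording change and a few more SAE reports to file. Sample size, visits and the planned analyses stay as they are, apart from one added count.

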6.9.1 Relationship of SAE to study drug or other intervention

The relationship of each SAE to the study intervention should be characterized using one of the following terms in accordance with ASRI-WPAHS IRB Guidelines: definitely, probably, possibly, unlikely or unrelated.

6.10 IRB/IEC Notification of SAEs and Other Unanticipated Problems

The Investigator will promptly notify the IRB of all on-site unanticipated, serious Adverse Events that are related to the research activity. Other unanticipated problems related to the research involving risk to subjects or others will also be reported promptly. Written reports will be filed using the IRB system and in accordance with the IRB SOP#11. External SAEs that are both unexpected and related to the study intervention will be reported promptly after the investigator receives the report.

6.10.1 Follow-up report

If an SAE has not resolved at the time of the initial report and new information arises that changes the investigator's assessment of the event, a follow-up report including all relevant new or reassessed information (e.g., concomitant medication, medical history) should be submitted to the IRB. The investigator is responsible for ensuring that all SAE are followed until either resolved or stable.

7 STUDY ADMINISTRATION

- 7.1 Data Collection and Management Data Sources
- **7.1.1** Initial recruitment of study participants will be at the discretion of the participating surgeons, as they will be involved in the decision to proceed with surgery, along with the patient.
- **7.1.2** Study participation will in no way affect the surgical decision making of the surgical provider. Once the patient has agreed/consented to participate in the study, the Epic Electronic Medical Record System will be used to record variables such as physical examination, imaging, surgery type, etc. The office visits and operative reports will be used to record the surgeon's observations and interventions.
- **7.1.3** Paper versions of the AOFAS and SF-36 surveys will be uploaded into the patient charts in Epic on password protected AHN computers. The paper version of these

forms will be kept in a locked file cabinet which is locked in the research coordinators office.

- **7.1.4** A backup of the data will also be stored on a pass key protected external hard-drive provided by the West Penn Hospital Foot and Ankle Residency Program.
- **7.1.5** All subjects in each arm of the study will be given a unique study number, linking them to the patient MRN number in the Epic system.
- **7.1.6** All data will be retained and destroyed after publication in accordance with institutional policy, SOP 072, IRB Record Retention, which is 10 years.

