There is also extensive evidence that midfoot fusions such as the Lapidus procedure have had good results following immediate or early weight-bearing. Blitz et al. were able to challenge the traditional postoperative non-weight-bearing period by using a 2 or 3 crossed screw fixation technique and allowing the patient to protected weight bear after approximately two weeks. Using both a curettage joint prep technique by one surgeon and planar resection by another surgeon, the joints were prepped to bleeding bone and then fixated with two crossing screws using lag technique. A third screw was used across the 1st and 2nd cuneiforms depending on surgeon judgment for adequate fixation. The results of these procedures were reviewed retrospectively. Of the 80 feet in which the results were reviewed, protected weight-bearing began at a mean of 14.8 days postop, with 100% going on to successful union at a mean time of 44.5 days. (3) Basile et al. investigated the outcomes of patients undergoing Lapidus who were allowed immediate weight-bearing in a removable boot with those made non-weight-bearing in a short leg cast for 6 weeks. They assessed first intermetatarsal angle and first ray elevation measurement radiographically immediately postoperative and then at the 6-month postoperative visit. In a total of 41 feet, there were no significant radiographic changes between the two groups in regards to radiographic evaluation and no non-unions or mal-unions were observed in either group. (4) Using a plantar oriented plate for Lapidus fixation, Gutteck et al. analyzed results between restricted weight-bearing with floor contact (NWB) and immediate full weight-bearing (FWB), both in short arthrodesis shoes. They reviewed 17 cases in each group and found there was no statistically significant difference in radiographic results, AOFAS scores or visual analog scale scores. They did, however, show there was a significant difference in time to return to work, as the FWB group was fit to return to work at a mean of 30.8 days postoperatively, while the NWB group averaged 57 days. (5)

There is also substantial evidence early or immediate weight-bearing is an alternative following trauma. Maffulli et al. performed a comparative longitudinal study placing patients undergoing open repair of midsubstance Achilles tendon tears into two groups, an

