
a plaster cast for 2 weeks, followed by a boot with traditional wedge progression until they reached a plantigrade orientation after 4 additional weeks. In their microdialysis analysis, they found that the healing tendons in both groups exhibited increased levels of metabolites glutamate, lactate, and pyruvate, compared to the subject's contralateral tendon, but the functional weight-bearing group had a significantly higher concentration of glutamate compared to the non-weight-bearing cast group. This correlated to improved functional outcomes at 6 months, and supported their conclusion that functional weight-bearing enhances early healing response after Achilles tendon repair. (10)

In the review of the literature, two separate systemic reviews were identified, which support early weight-bearing after ankle fracture repair when compared to late weightbearing or non-weight-bearing for six weeks following surgery. These reviews found no significant adverse results in the early weight-bearing groups, while finding earlier return to previous activities and earlier return to work. (11,12). Additionally, Assal et al. was able to show that, with augmented fixation, early weight-bearing in older patients (greater than 70) with Weber B ankle fractures was a safe and satisfactory method of postoperative care. (13) Starkweather et al. found no malunions or nonunions, and a 9.5% complication rate in patients allowed to be protective weight-bearing following ankle fracture ORIF, while Firoozabadi et al. saw a complication rate of 8% and a loss of correction in only 1 of 26 (4%) patients allowed to immediately bear weight following ankle ORIF. (14, 15) In a randomized control trial, Dehghan et al. divided 110 patients into an early WB group (2 weeks) and a late WB group (6 weeks) and assessed time to return to work, SF-36 scores, and rates of complications. They found no difference in return to work between the two groups, but the early WB group showed significantly improved SF-36 scores on both physical and mental components. Early WB was also found to have similar wound complication rates, with no cases of fixation failure or loss of reduction. The late WB group additionally showed higher rates of hardware removal due to irritation. (19% vs 2%) (16)

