3 INVESTIGATIONAL PLAN

3.1 General Schema of Study Design

The study will be a randomized 1:1, controlled trial, prospective in nature, where participants undergoing foot and ankle surgery will be randomly placed into one of two

groups; an immediate weight-bearing group or a non-weight-bearing group. The patients will be randomly placed into the study group and control group if they meet all eligibility criteria. The first patient recruited will be assigned a unique study identifier (i.e., FAI001) and a coin flip will randomize the patient into either the study group (Heads) or control group (Tails). From that point, all patients will be placed into their groups by alternating between the control group and the study group. No bias will be placed on the subject or the procedure in regard to inclusion into a certain research group. Patients will be recruited and should they agree will be consented to the study with two year follow up results.

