4 STUDY PROCEDURES

4.1 Screening Visit

Below is a list of all of the procedures to be performed at each visit.

- Informed Consent
- Physical Exam
- Radiographic/Advanced Imaging
- Medical Record Review
 - Review of the medical record will include reviewing the past medical and surgical history, laboratory values, and most recent visits to other health care providers in the standard fashion of any office or inpatient encounter
- Surgical procedure discussed and operative consent
- Pre-operative AOFAS and SF-36 surveys completed

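### Allocation at the screening visit lets the operating surgeon know or predict the arm before choosing procedure and fixation, leaving a risk of performance bias

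*Combined protocol and SAP*

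**What the plan says.** - **Timing.** In Table 1 (Schedule of Study Procedures, in the abstract) the row "Randomization" has a single mark, under Screening, to the left of the Surgery column. The abstract defines the arms as two post-operative regimens: protected loading in a boot, or six weeks without loading.
- **Method.** Section 3.1 states "The patients will be randomly placed into the study group and control group if they meet all eligibility criteria". It decides the first patient by coin flip and continues: "From that point, all patients will be placed into their groups by alternating between the control group and the study group".
- **People.** The abstract has the primary investigator and/or co-investigator take consent in clinic. Sections 7.1.1 and 7.4 leave recruitment to the discretion of the participating surgeons. No section describes masking of surgeon, patient or assessor.
- **Stated protection.** Section 7.1.2, repeated in 7.4: "Study participation will in no way affect the surgical decision making of the surgical provider".
- **Link between loading and fixation.** Section 7.3.4 names possible added stress on the fixation as a risk of the study arm. Section 1.2 cites a series in which, "with augmented fixation, early weight-bearing in older patients (greater than 70" years) was found safe.
- **Baseline surveys.** Section 4.1 includes "Pre-operative AOFAS and SF-36 surveys completed" in its list for the screening visit. That list does not mention randomization.

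**The concern.** The interventions differ only after the wound is closed, so nothing in the design requires the arm to be known earlier. Once it is known, a surgeon who expects the limb to be loaded at once has a reason to operate differently, for instance by adding fixation. The trial would then compare immediate weight-bearing plus whatever surgery accompanied it with non-weight-bearing plus the usual surgery. That is not the question in sections 2 and 2.1.

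The outcomes most exposed are the secondary endpoints in section 6.2 that carry the safety claim: complications and osseous healing. A favourable result there could reflect the construct rather than the loading. The problem is separate from how the sequence is generated, because a perfectly concealed sequence opened at screening would still tell the surgeon the arm before the operation.

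**Working it through.** **1. Can the arm be known before surgery?** Three facts combine: allocation is at screening (Table 1), no masking is described, and the arms alternate (3.1). Under alternation only the first assignment is random. The other 230 − 1 = 229 are fixed by the one before, so anyone who knows the last assignment knows the next. Early knowledge is therefore possible by disclosure or by prediction.

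**2. Does anything stop that knowledge from affecting surgery?** Sections 7.1.2 and 7.4 state an intent. No section requires the planned procedure or fixation to be recorded before the arm is known. The readable part of the data form in the Appendix has a study-group field on the sheet that carries the pre-operative scores. It lists procedures but shows no field for fixation.

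**3. Would the analysis remove it?** Section 6.4.1 adjusts SF-36 and AOFAS scores for age, gender, BMI and diabetes, not for procedure, fixation or surgeon. Fixation chosen after allocation is also a post-randomization variable, so adjusting for it would not fully restore the comparison.

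**4. The plan's own figure.** Inputs from section 6.5: d = 0.40, two-sided alpha 0.05, 100 evaluable per arm, power 80%.
- Normal approximation: n = 2(1.960 + 0.842)² / 0.40² = 98.1, so 99 per arm.
- Power at 100 per arm: standard error √(2/100) = 0.1414 SD; Φ(0.40/0.1414 − 1.960) = 80.7%.
- Exact t: 99.1, so 100 per arm; power 80.4%.

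The stated 100 per arm reproduces. No figure in the plan is disputed.

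**5. Illustration on assumed values.** The documents give no size for a technique effect. Let b be the difference in mean score, in SD, produced only by surgery differing between arms: b = (difference in share of patients receiving the technique) × (its effect in SD). Shares differing by 10 to 30 points and effects of 0.25 to 0.75 SD give b from 0.10 × 0.25 = 0.025 to 0.30 × 0.75 = 0.225. For example, 0.20 × 0.5 = 0.10.

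At 100 per arm:
- Rejection with no weight-bearing effect = Φ(b/0.1414 − 1.960) + Φ(−b/0.1414 − 1.960).
- Power when the shift opposes a true 0.40 = Φ((0.40 − b)/0.1414 − 1.960).

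| b (SD) | Rejection, no true effect | Power, shift opposing d = 0.40 |
|---|---|---|
| 0 | 5.0% | 80.7% |
| 0.05 | 6.4% | 69.7% |
| 0.10 | 10.9% | 56.4% |
| 0.15 | 18.6% | 42.4% |
| 0.20 | 29.3% | 29.3% |

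The table shows what a shift would do to a primary score if one occurred. It does not show that one will.

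**The case against.** **What stands.** No section says when or to whom the arm is disclosed, or that any surgeon changes fixation by arm. Consent and recruitment are assigned to overlapping but not identical roles, so the surgeon's knowledge is a strong inference, not stated text. Operative reports will record the surgeon's interventions (7.1.2), the regression in section 6.4.1 includes surgical characteristics, and the safety review in 7.3.1 considers the procedures performed. A difference in technique could thus be made visible, though none of this prevents it and no comparison of fixation by arm is planned.

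**Stronger readings that the documents do not support.**
- *That weight-bearing is confounded with surgical technique.* Surgical choice follows allocation, so the accurate term is performance bias, and it is a risk left open rather than an event shown.
- *That all 230 operations are affected.* The trial includes soft-tissue procedures, and the form lists tendon repairs and transfers, where a stronger bony construct need not apply.
- *That section 1.2 shows fixation being strengthened for early loading in general.* In the midfoot series, "A third screw was used across the 1st and 2nd cuneiforms depending on surgeon judgment for adequate fixation". That series had no comparison of weight-bearing arms, so the extra screw was not a response to one. Only the augmented-fixation series is on point, and it concerns one ankle-fracture type in patients over 70.
- *That a bias in complications can be computed from the 9.5% rate in section 1.2.* Assuming stronger fixation halves risk and is used in 10, 30 or 50 points more of the study arm, 9.5% × (1 − 0.5p) gives 9.0%, 8.1% or 7.1%. The arithmetic is right, but the halving and the shares are not in the documents. The 9.5% also comes from ankle-fracture patients who were all allowed to bear weight, so it is not a control rate. In absolute terms the falls are about 0.5, 1.6 and 2.7 patients of 115.
- *That patients rate baseline after learning their arm.* Section 4.1 is a list without a stated order. That the surveys come last in it proves nothing; the order is simply undefined.

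**Conclusion.** The point holds as a design weakness that should be fixed. It does not by itself invalidate the trial. The timing, the absence of masking and the lack of a mechanism behind the stated intent are plain in the documents. That the operating surgeon will know the arm is a strong inference from them. That surgery will then differ by arm is plausible on the protocol's own reasoning in section 7.3.4 and one series in section 1.2, but it is not demonstrated.

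The exposure lies chiefly in complications and osseous healing for procedures that use fixation. Its size cannot be derived from the documents, and the shifts of 0.05 to 0.20 SD used above are assumptions. The survey-order issue is a lesser gap that one sentence closes.

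**What to change.** 1. **Table 1:** move the randomization mark from Screening to the Surgery column. Consent and eligibility review stay at screening.
2. **Sections 3.1 and 4.2.1:** state that the arm is assigned and disclosed only after the operation is finished and the procedure and fixation are recorded.
3. **Section 3.1:** replace alternation with a concealed random sequence, for example in sealed opaque envelopes. This must accompany the change of timing, because later allocation alone does not help while the next arm is predictable.
4. **Section 4.1:** state that the pre-operative AOFAS and SF-36 are completed before allocation.
5. **Section 6.4.1:** report fixation by arm from the operative reports already collected under 7.1.2.

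**Cost.** The 100 evaluable per arm, the total of 230 and the visit schedule are unchanged. Patients must be counselled and equipped before surgery for either arm, a modest burden since the abstract already excludes those unwilling to accept either. Someone must release assignments on the day of surgery at each of the five sites, two of which are surgery centers.

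**If same-day release proves unworkable at a site,** a lighter but weaker option is to record the planned procedure and fixation before the arm is revealed, still with a concealed sequence. Departures from the plan could then be seen by arm, but not prevented.
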